8.4 Sample Size

The sample size will be a minimum of 170 prospectively enrolled subjects. This sample size will provide data upon which to obtain a 5-year survivorship estimate from newly enrolled subjects who did not participate in the COC36 IDE study. The sample size of 170 subjects in this PAS is approximately the same sample size of COC36 IDE investigational subjects, and hence will provide sufficient data on a new cohort of subjects to further support mid-term clinical success.

The objective of this study is to obtain an estimate of device survivorship at 5-years post-operatively. The enrolled 170 enrolled subjects will provide a minimum of 136 subjects (80% of enrolled subjects) with 5-year follow-up. This will yield a 5-year survivorship estimate that has an approximate 3.6% margin of error. In particular, Peto's estimate¹ for the variance of a Kaplan-Meier survival estimate is

$$\text{var}(\hat{S}(t)) = \frac{(\hat{S}(t))^2(1 - \hat{S}(t))}{n(t)}$$

where $\hat{S}(t)$ is the estimate of survival at time t and $n(t)$ is the number of unrevised subjects at risk (still being followed) at time, and t . Hence, if it is assumed that the point estimate of survival is at a minimally acceptable level of 95.1% for subjects in this PAS, and there is a minimum of 136 subjects (80% of enrolled subjects) at 5-years post-operatively upon which this estimate is based, then an estimate for the variance of the Kaplan-Meier survival estimate at 5 years is

$$\text{var}[\hat{S}(5)] = \frac{[0.951]^2(0.049)}{136} = 0.00034,$$

and a two-sided 95% confidence interval margin of error for survival at 5 years is anticipated to be approximately $1.96 * \sqrt{0.00034} = 3.6\%$.

A sample size of 170 enrolled subjects is therefore justified in order to obtain a 3.6% margin of error on a 5 year survivorship estimate.

8.5 Anticipated Number of Subjects with Minimum 5 Year Follow-up

A minimum of 80% of enrolled subjects (136 subjects) will be confirmed to either have a surviving implant or to have had a revision at a minimum of 5 years post-op with a clinical evaluation.

8.6 Treatment Assignment

The 36 mm COC device is the only device configuration of interest in the study.

¹ Cantor, A. Estimates of the Variance of the Kaplan-Meier Estimator. In: *Extending SAS® Survival Analysis Techniques for Medical Research*. 2nd ed., Cary NC: SAS Institute, 2003:24.

8.7 Secondary Endpoints

Secondary endpoints include Harris Hip score and sub-score means, radiographic evaluations, device survivorship, and adverse event outcomes at each protocol defined post-op interval. Cumulative results of these endpoints will be reported in each interim PAS report to FDA.

8.8 Interim Analysis

There are no planned interim analyses for the purpose of terminating the study early. However, some statistical analyses may be performed for conference presentations or abstracts prior to the primary endpoint being reached.

Interim analyses of the primary and secondary endpoints will be carried out for each interim PAS report to FDA.

8.9 Analysis Plan

At the time of each interim PAS report, the following analyses will be presented for all subjects combined, as well as separately for each individual stem type that is represented in the PAS, and also separately for each individual cup type that is represented in the PAS:

- Baseline summary statistics will be calculated for age, weight, BMI, race, ethnicity and pre-op Harris Hip Scores for both cohorts. The proportion of each gender will be calculated.
- Harris Hip score summary statistics and change from baseline statistics will be reported for each protocol defined post-op visit interval. These will be provided for total Harris Hip score as well as the Harris Hip sub-scores (pain, function, activity, deformity, and range of motion). These will be provided for total Harris Hip score as well as the Harris Hip sub-scores. Results will be presented overall, as well as stratified by obesity (non-obese vs. obese) according to BMI (subjects with $BMI < 30$ and with $BMI \geq 30$, respectively)².
- Subject-reported outcomes will be reported for each protocol defined post-op visit interval.
- Radiographic analysis will be reported for each protocol defined post-op visit interval.
- Tabular displays of all cumulative reported adverse events will be provided by adverse event, as well as by category (intraoperative, postoperative-operative site, systemic, and overall). Tables will also be provided of adverse events over time.
- A Kaplan-Meier survivorship analysis will be provided, with device survivorship as a function of post-op time. A proportional hazards model will be provided, in which device survivorship is a function of post-op time, and with BMI (at the time of index surgery) as a covariate. Implant survival will be reported over time where greater than 40 hips are still at risk of revision.
- For Subjects that are not able to return to clinic at the 3- or 4-year interval, device survivorship information will be obtained through telephone interviews and will be utilized in the Kaplan-Meier analysis of device survivorship for the primary endpoint analysis in the study.

² Obesity is defined as $BMI \geq 30$ According to the World Health Organization:

<http://www.who.int/mediacentre/factsheets/fs311/en/>

Confidential
May 11, 2020

DePuy Synthes
CIP#12017 Revision D

8.10 Institutional Review Board

Prior to enrolling subjects into the study, each participating Investigator will be required to obtain approval from the reviewing institutional review board (IRB) at each institution where the study will be conducted. It is the Investigator's responsibility to submit and obtain IRB approval of the study plan, the Informed Patient Consent form (IPC), and any relevant study related information.

Revisions or amendments to the study plan and/or the IPC form that affect the scientific soundness of the post-approval study or the rights, safety or welfare of the participating subjects require approval by the reviewing IRB and the study sponsor prior to being implemented.

8.11 Informed Patient Consent (IPC) and Authorization for Release of Medical Records

An informed patient consent must be obtained for all subjects in person prior to enrollment into this 36 mm COC Post-Approval Study. Subjects who agree to participate will complete an IRB-approved IPC that documents his or her willingness to take part in this post-approval study. Each potential subject will have the nature and the purpose of this clinical investigation explained to him or her by the Clinical Investigator or another member of the investigative team at the site. The investigator will explain the following features of the study to the patient thoroughly and will offer to answer any questions the patient may have.

- The purpose of the study
- Possibility of failure and subsequent treatment(s)
- Alternative procedures
- Requirements of the study (follow-up visits)
- The plan to perform retrieval analysis in the event of an explanted device
- A modest payment may be provided to cover subject travel expenditures associated with study participation to 5-years.

Prior to entry into this clinical investigation the patient must give voluntary, written informed patient consent to participate by signing the IPC. A copy of the IPC is to be provided to the subject. A study subject is enrolled once they have signed the IPC and had the study device implanted.

8.12 Financial Disclosure

Each Investigator participating in the study will complete a financial disclosure form at the beginning of the study and then per DePuy Synthes' policy thereafter. Per FDA requirements, an additional financial disclosure must be completed one year after the study has concluded.

9 POST APPROVAL STUDY PLAN

9.1 Subject Population

For the purpose of this study, a Subject is defined as an individual who participates in the clinical study as a recipient of the investigational product. Note: before the IPC is obtained, a Subject is referred to as a “patient”.

The post-approval study (PAS) will be comprised of:	Prospectively enrolled subjects in this COC36 PAS study who meet the eligibility criteria described below and are willing to provide written informed consent.
---	--

The Investigator or designee will solicit the IPC of any patient meeting the eligibility criteria and will explain the features of the study and answer any questions from the patient.

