9.7 Enrollment & Subject Identification Number

A study subject is **enrolled** when they have met eligibility criteria, been consented and had the THA procedure and study device implanted per protocol. Once enrolled, the site assigns the subject ID number which is comprised of a two-digit site code followed by a 4- digit subject specific code. For example, the first three enrolled subjects at site #06 would be: 06-0401, 06-0402, 06-0403.

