Interim Visits	
An interim office visit is defined as any visit at the study site where a study Subject is seen by one of the site staff including the Principal Investigator (PI), any sub-investigator (as appropriate), and anyone identified on the PI's team, outside of the scheduled study visit. An interim visit is only to be reported when the visit falls between study intervals as described in Table 4. An Interim Visit CRF is not to be completed if the Subject comes in for additional, unplanned visits in the "in-window" study interval.
 
If the previous protocol-defined, study interval visit was missed, the required CRFs in that previously-missed interval visit are also required along with the Interim Visit CRF.
 
If the interim visit is related to a new, worsening, or resolved adverse event, both an Adverse Event CRF and Interim Visit CRF are completed.

End of Study/ Withdrawal	
This form must be completed for all enrolled subjects to either reflect
 
 • Completion of final endpoint (Minimum 5 years) • Premature withdrawal 
Study participation may be prematurely discontinued through revision of acetabular components (shell and/or liner), withdrawal of consent, or death.
 
➤ NOTE: A revision is defined as a surgical procedure of the affected hip where one or more of the THA components (femoral stem, femoral head, acetabular shell and/or acetabular liner) are removed. Of note, if both the acetabular shell and ceramic liner remain intact, the Subject will continue to be followed in the study.
 
➤ NOTE: Should it be necessary for the Subject to undergo a revision of either the acetabular shell and/or the acetabular liner between the date of the enrollment and the completion of the study data acquisition, the Subject is withdrawn from study participation. Thus, both an Adverse Event (AE) CRF and an END of Study/Withdrawal CRF would be completed.

Electronic Case Report Forms (CRFs) entered into an electronic data capture (EDC) system will be used to collect all Subject data once a Subject is enrolled in the study. Study sites will be instructed to enter Subject data on to the CRFs via the EDC web-based database portal.

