10 RISK ANALYSIS

10.1 Potential Adverse Events (AEs)

Adverse Events (AEs) must be reported for all Subjects and AE determination will be done by the Principal Investigator, or appropriate designee.

Potential AEs include:

- Excessive wear of the ceramic components secondary to damage of mating wear surfaces or debris particles;
- Metal sensitivity reactions;
- Possible detachment of the coating(s) on the femoral stem or acetabular shell components, potentially leading to increased debris particles;
- Device related noise such as, clicking, popping, squeaking or grinding;
- Pain;
- Femoral or acetabular perforation, or bone fracture while seating the device;
- Damage to blood vessels resulting in hematoma;

- Temporary or permanent nerve damage resulting in pain or numbness of the affected limb;
- Undesirable shortening or lengthening of the limb;
- Traumatic arthrosis of the hip from intraoperative positioning of the extremity;
- Cardiovascular disorders including venous thrombosis, pulmonary embolism, or myocardial infarction;
- Temporary or permanent neuropathies;
- Delayed wound healing;
- Infection;
- Osteolysis;
- Fracture, migration, loosening, subluxation, or dislocation of the prosthesis or any of its components, any of which may require a second surgical intervention or revision;
- Periarticular calcification or ossification, with or without impediment to joint mobility;
- Inadequate range of motion due to improper selection or positioning of components, by femoral impingement, and periarticular calcification; and
- Death.

These possible AEs are not unique to the CERAMAX® Ceramic Hip System and, as stated above, may occur with any total joint replacement surgery.

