10.2 Potential Adverse Events (AEs) Associated with the CERAMAX® Ceramic Hip System

The most commonly reported adverse events related to the DePuy Synthes CERAMAX® Ceramic Total Hip System are:

- Wear of the ceramic acetabular components has been reported following total hip replacement. Higher rates of wear may be initiated by particles of cement, metal, or other debris that can cause abrasion of the articulating surfaces. Higher rates of wear may shorten the useful life of the prosthesis, and lead to early revision surgery to replace the worn prosthetic components.
- While rare, fatigue fracture of the prosthetic component can occur as a result of improper assembly, trauma, strenuous activity, improper alignment, or duration of service.
- Component dissociation.
- Breakage or chipping of the ceramic femoral head and/or ceramic acetabular insert.

There are no additional risks to the subject associated with participation in this study. The evaluations included in the study are considered to be the standard of care for following total hip replacement patients. Likewise, there is no personal benefit to the subject for participation in this study. However, data collected in this study will contribute to the safety profile of this Ceramic on Ceramic articulation.

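### A consented patient whose 36 mm ceramic bearing is attempted and then abandoned during surgery has no place in the intraoperative safety data

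*Protocol*

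**What the plan says.** **Who is a Subject.** Protocol 9.1 states that "a Subject is defined as an individual who participates in the clinical study as a recipient of the investigational product". A note in the same section says that the person is called a patient until consent is given, which suggests that Subject status begins at consent.

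**Who is enrolled.** Protocol 8.11: "A study subject is enrolled once they have signed the IPC and had the study device implanted". Protocol 9.7 requires that the person is eligible, has "been consented and had the THA procedure and study device implanted per protocol", and continues: "Once enrolled, the site assigns the subject ID number".

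**Whose data are collected.** The text after Table 3 in Protocol 9.9 says that electronic case report forms "will be used to collect all Subject data once a Subject is enrolled in the study". Protocol 10.1: "Adverse Events (AEs) must be reported for all Subjects". Protocol 10.5 starts adverse event reporting at surgery.

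**Who is analysed.** SAP section 6 defines one set, the Safety Analysis Set, for patients who consented and were treated according to the protocol. All analyses use it. SAP section 2 describes every subject as having received the 36 mm device.

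**Which events are at stake.** Protocol 10.2 lists, among events associated with this system, "Breakage or chipping of the ceramic femoral head and/or ceramic acetabular insert". Protocol 8.9 plans adverse event tables by event "as well as by category (intraoperative, postoperative-operative site, systemic, and overall").

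**The concern.** The study's stated aim is information on the performance and safety of the device. Some intraoperative device problems end with a second 36 mm ceramic part in place; others end with the ceramic bearing abandoned. Under these rules the first kind is recorded and the second is not. Entry to the safety data then depends partly on the outcome being measured, and the events lost are those in which the device could not be used at all. An intraoperative table built this way can only err towards fewer events. A reader of the report could not tell, because SAP 8.2 has no disposition row for patients who consented and were operated on but were not enrolled.

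**Working it through.** No figure in the plan bears on this point, so the check is a trace of the rules. Take two consented, eligible patients whose ceramic insert chips while being seated. Patient A receives another 36 mm ceramic insert. Patient B leaves with a different bearing, with the PINNACLE shell and a permitted stem still in place.

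| Step | Source | Patient A | Patient B |
|---|---|---|---|
| Consent signed | Protocol 8.11 | yes | yes |
| Study device implanted | Protocol 8.11, 9.7 | yes | no |
| Enrolled, subject ID assigned | Protocol 9.7 | yes | no |
| Electronic CRF data collected | Protocol 9.9 | yes | no |
| Subject for adverse event reporting | Protocol 9.1, 10.1 | yes | no by the definition, arguably yes by the note |
| In the Safety Analysis Set | SAP 6 | yes | no, on the natural reading |
| Counted in disposition | SAP 8.2 | yes | no row |

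The retained shell and stem do not change the second row for B. Protocol 7.1 builds the system around the 36 mm ceramic insert and head, and Protocol 8.6 and SAP 2 name the 36 mm ceramic-on-ceramic configuration as the only one of interest.

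Three places use looser wording: the note in 9.1; Table 2, which ticks the adverse event and withdrawal forms at the pre-operative visit; and Protocol 13, which treats enrolled and consented as the same thing. None of them gives patient B an ID, an electronic record or a place in the analysis set.

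**Size.** The documents give no conversion rate, so the following is an assumption shown over a range. With k abandoned implantations in addition to the 170 enrolled, the proportion of attempts abandoned is k/(170 + k), with an exact binomial interval (the method SAP 8.7 uses for adverse events):

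| k (assumed) | k/(170 + k) | Exact 95% interval |
|---|---|---|
| 1 | 1/171 = 0.6% | 0.01% to 3.2% |
| 2 | 2/172 = 1.2% | 0.1% to 4.1% |
| 3 | 3/173 = 1.7% | 0.4% to 5.0% |
| 5 | 5/175 = 2.9% | 0.9% to 6.5% |

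Whatever k is, the enrolled cohort shows 0/170 abandoned implantations. The exact upper limit for 0/170 is 1 − 0.025^(1/170) = 2.1%, but that zero follows from the enrolment rule and is not an observation.

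**Primary endpoint.** Protocol 8.2 estimates survivorship of implanted hips, with failure defined as removal of a component. Protocol 8.3 derives its level from a constant yearly revision hazard of 1%: S(5) = exp(−0.05) = 0.951. That curve starts at S(0) = 1 and has no day-0 component. A bearing that was never left in place is outside this estimand.

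**The case against.** The strongest reply is that no sentence excludes these patients. The exclusion is inferred from several rules read together, and the 9.1 definition is a weak support because its own note points the other way. On this view the fault is loose wording. That stands as a description of 9.1. The explicit condition, however, is in 8.11 and 9.7, and a site that follows those sections has no ID under which to enter the event.

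A second reply is that the sponsor may learn of such cases by other routes. Table 5 sends device deficiencies, including malfunctions and use errors, to the sponsor's complaint unit; 9.6 sends screening logs to the sponsor; and section 14 puts screening and recruitment logs in the FDA reports. This also stands, so a reader should not infer that these events go wholly unseen. But nothing in the documents brings those sources into the study's adverse event tables. The CRFs, log templates and anticipated-event list are exhibits that cannot be seen here, so whether a log has a field for an abandoned implantation cannot be checked.

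A third reply is that entry restricted to implanted patients is a defensible choice for a non-comparative survivorship study. For survivorship that is right.

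Two stronger readings are tempting, and the documents support neither. One is that conversions should be counted as day-0 failures and would pull the 5-year estimate below 95.1%. That mixes a different event with an endpoint defined as revision of implanted hips, and a conversion may have reasons other than failure of the device. The other is that intraoperative rates are driven to zero. They are not: events in patients who still receive the device, including a chipped insert replaced by another 36 mm ceramic insert, stay within the adverse event reporting rules.

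**Conclusion.** The point holds for intraoperative safety. Following the plan as written, a consented patient whose 36 mm ceramic head or insert is attempted and abandoned is missing from the adverse event tables and from disposition. Intraoperative adverse event rates, and any device-deficiency rate reported from the study, can therefore be understated. The direction follows from the rules; the size is unknown, and the counts above are illustrations only. The primary Kaplan-Meier estimate is not affected. The conclusion assumes that sites apply 8.11 and 9.7 literally, and that no exhibit withheld from the public documents provides for these patients.

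**What to change.** 1. **Protocol 8.11, 9.1, 9.7 and 10.5.** Reconcile the Subject and enrolment wording so that operative details, device log and adverse event data (CRFs 6, 7 and 9) cover every consented patient in whom implantation of the 36 mm ceramic head or insert was attempted, whether or not the ceramic bearing was left in place. The trigger should be the ceramic head or insert. A rule that applied only when no study component remained would miss a patient who keeps the shell or stem.
2. **SAP 6 and 8.7.** Add an attempted-implantation safety set and use it for intraoperative adverse events and device deficiencies.
3. **SAP 8.2.** Report the number of conversions and their reasons in disposition.
4. **If surgery is already complete.** This looks likely, since the SAP is dated 20 December 2023 and describes treatment in the past tense. Recover the cases from screening logs, operative records and complaint files where consent permits. Failing that, state in the report that intraoperative rates exclude abandoned implantations.
5. **Keep the Kaplan-Meier analysis on implanted subjects.**

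The cost is a wording amendment, one more analysis set and the retrieval of what should be a few records for patients who have no subject ID. Retrieval depends on the consent terms, which cannot be seen here. Intraoperative rates may look slightly less favourable.

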9.2 Indication for Use

Subjects will be entered into this study if they meet the criteria for inclusion described below. Subjects who have an existing contra-lateral total hip replacement at the time of consent may also be entered into this study if they qualify based upon the criteria for inclusion and the approved labeling requirements.

9.3 Subject Eligibility

The eligibility criteria will be consistent with the approved labeling for the COC36 device (**Exhibit H**).

Individuals meeting all of the following specific criteria will be considered for participation in the study:

9.4 Inclusions:

1. Males and females between 21 - 75 at the time of surgery.
2. Individuals, who in the opinion of the investigator, are suitable candidates for primary total hip replacement using the devices specified in this protocol.
3. Individuals with non-inflammatory degenerative joint disease (NIDJD) or any of its composite diagnoses of osteoarthritis, avascular necrosis, and posttraumatic arthritis.
4. Individuals who are willing and able to provide informed patient consent for participation in the study;
5. Individuals who are willing and able to return for follow-up as specified by the study protocol; and
6. Individuals who are willing and able to complete the Subject Hip Outcomes questionnaire as specified by the study protocol.

9.5 Exclusions:

Subjects will be excluded if in the opinion of the Investigator, the individual meets any of the following exclusions:

1. Skeletally immature patients (tibial and femoral epiphyses not closed)
2. Evidence of active infections that may spread to other areas of the body (e.g., osteomyelitis, pyogenic infection of the hip joint, overt infection, urinary tract infection, etc.)

3. The presence of any known neoplastic (tumor-causing) or metastatic (spread of cancerous cells) disease
4. Significant neurologic or musculoskeletal disorders or diseases that may adversely affect gait, weight bearing or postoperative recovery (e.g., muscular dystrophy, multiple sclerosis)
5. Presence of highly communicable disease(s) that may limit follow-up (e.g., immuno-compromised conditions, hepatitis, active tuberculosis, etc.)
6. Any condition that may interfere with postoperative recovery (e.g., Paget's disease, Charcot's disease)
7. Inadequate bone stock to support the device (e.g., severe osteopenia or osteoporosis)
8. Poor skin coverage around the hip joint
9. Use in patients with known allergies to the implant materials
10. Marked atrophy (muscle and/or tissue loss) or deformity in the upper femur such as a birth defect affecting the leg bones.
11. Inflammatory degenerative joint disease (e.g., rheumatoid arthritis)
12. Subject has participated in an IDE/IND clinical investigation, other than the COC28/COC36 IDE or PAS for their contralateral hip, with an investigational product in the last three months.
13. Subject is currently involved in a personal injury litigation, medical-legal or worker's compensation claims.
14. Subject is a known drug or alcohol abuser or has a psychological disorder that could affect their ability to comply with protocol procedures and/or subject-completed questionnaires.
15. The Subject is a woman who is pregnant or lactating.
16. The Subject has a medical condition with less than 2 years of life expectancy.

